We will contract with NORC at the University of Chicago to recruit 1,230 young adults (aged 18-29) from a combination of their AmeriSpeak panel (approximately N=1000) and a third-party opt-in panel (remainder). NORC will recruit participants, program the survey, administer the survey to eligible participants, and provide the Wake Forest team with a final dataset, where participants are weighted to create a nationally representative sample. Participants who complete the survey will receive a small incentive, as agreed up by their panel, generally worth a few dollars. Participants will complete demographics and tobacco use measures and then will be randomized to one of three conditions. One-third (about 410 participants) will be randomized to the pictorial warning intervention group, 410 to the text-only warning intervention group, and 410 to the no-warning control group. The two intervention groups will see six respective warnings on sample packaging, one at a time. The control group will see the sample packaging once, without a warning. Intervention group participants will respond to measures designed to assess their warning reactions (emotional and cognitive reactions, perceived message effectiveness), and appeal of each package. Control group participants will complete items on package appeal. After viewing all warnings, participants will complete items on behavioral intentions, perceived risks of waterpipe smoking, and knowledge of risks. After completing the study, participants will be provided with a link to the CDC fact sheet about waterpipe smoking and the tobacco quit line number.

Setting

Participants will complete the survey on a computer, tablet, or phone at a location of their choosing.

Subject Selection Criteria

We will conduct an online national probability-based survey with a sample of 1,230 US young adults (18-29 years old) using the AmeriSpeak panel at NORC and a third-party non-probability sample, weighted with the AmeriSpeak sample to be nationally representative.

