Participants will be randomized to one of three conditions: text-only warnings, pictorial warnings, no warning control. Participants in the two intervention conditions will be shown six waterpipe packages, each with a different warning corresponding to their condition, in random order, and will complete items on package appeal and warning perceptions. Participants in the control condition will be shown one waterpipe package with no warning on it and will complete items on package appeal. The waterpipe package is a fictitious brand created by the study team in a separate study. All elements of the waterpipe packaging will be the same across conditions and the only difference will be the presence and type of warning.

Outcome Measure(s)

PRIMARY

Behavioral Intentions. The primary outcome is intention to smoke tobacco in a waterpipe within the next year, measured by averaging three items adapted from research on cigarette smoking:

1. How interested are you in smoking hookah in the next year?
2. How likely are you to smoke hookah in the next year?
3. How much do you plan to smoke hookah in the next year?

Response scale: (1) Not at all / (2) Very little / (3) Somewhat / (4) Quite a bit / (5) Very

SECONDARY

None

OTHER

Product Appeal. Three items will be used to measure how appealing each waterpipe tobacco package is to respondents, how likely they would be to try the product, and how much the packaging makes the respondent think that the product is harmful.

1. How appealing is this product to you?

2. How likely would you be to try this product?
3. How much does this packaging make you think this product is harmful?

Response scale: (1) Not at all / (2) A little / (3) Somewhat / (4) A lot

Mean Perceived Message Effectiveness (PME). This outcome will be measured using the 3-item Perceived Measured Effectiveness scale created by Noar and colleagues that includes items on attitudes, risk beliefs, and intentions. Overall scores are determined by summing the scores of the three items and dividing by three.

1. How much does this warning make smoking hookah seem unpleasant to you?
2. How much does this warning make you concerned about the health effects of smoking hookah?
3. How much does this warning discourage you from wanting to smoke hookah?

Response scale: (1) Not at all / (2) Very little / (3) Somewhat / (4) Quite a bit / (5) A great deal

Attention. One item to measure self-reported attention to the warning.

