There are three goals for the analysis. First, compare WTS intentions between those exposed to text versus pictorial waterpipe warnings. We hypothesize that those exposed to pictorial warnings will have lower WTS intentions than those exposed to text warnings. To test the differences in warnings format on WTS intentions, we will fit a linear regression model using PROC MIXED in SAS to account for the sampling design features (e.g., sample weights, repeated measures). We will then examine experimental condition as a fixed effect with and without adjustment for potential confounders (e.g. sex, race/ethnicity, age, SES, WTS, use of other tobacco products). All tests will be two-sided. For a sample of 400 participants per condition, we will have 80% power to detect differences between the text only and pictorial conditions in waterpipe intentions of 0.24 or greater (corresponding to an effect size 0.16) in a design with 6 repeated measurements having a compound symmetry covariance structure when the standard deviation is 1.5, based on Lipkus & Mays (2018). For comparisons between the text or pictorial warnings and the control condition (which does not have repeated measures), we will have 80% power to detect differences of 0.27 or greater, corresponding to an effect size of 0.18. For all comparison, the correlation between repeated observations on the same subject is 0.6 and the alpha level is 0.05. As a sensitivity analysis, we will perform a subgroup analysis restricted to those reporting that they have not participated in a tobacco study in the past year to examine whether prior participation influences our findings. Second, we will assess the impact of warnings on behavioral antecedents, such as negative affect, cognitive elaboration, perceived risks, and knowledge using separate models, similar to those described above for WTS intentions. Third, we will select four coordinating warnings from each condition (same text in both), with the highest PME scores for use in Aim 3. We will assess the rank order of warnings based on PME scores for the sample as a whole and for subgroups, based on sex, race/ethnicity, sexual orientation, and WTS behavior to determine whether the rankings remain consistent. Ultimately, we will select four text and four pictorial warnings (that match) and are consistently ranked high on PME across subgroups.

Human Subjects Protection

Subject Recruitment Methods

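### Warnings are rated in random order, but viewing position is in no stated analysis, which costs some precision in the PME contrasts and rankings that choose the Aim 3 warnings

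*Combined protocol and SAP*

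**What the plan says.** Interventions and Interactions has each intervention participant view six packages, "each with a different warning corresponding to their condition, in random order, and will complete items on package appeal and warning perceptions". Control participants see one package, once, without a warning, and rate its appeal.

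The Analytical Plan describes the model for intentions as one that will "examine experimental condition as a fixed effect with and without adjustment for potential confounders (e.g. sex, race/ethnicity, age, SES, WTS, use of other tobacco products". The list is only illustrative, and every example in it is a participant characteristic. Behavioural antecedents are analysed "using separate models, similar to those described above for WTS intentions".

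On choosing warnings for Aim 3, the plan says "We will assess the rank order of warnings based on PME scores for the sample as a whole and for subgroups". It names no model for the ranking and does not list individual warning as a factor in any model. Viewing position appears neither as a covariate nor as a variable that NORC must deliver.

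On the timing of the primary outcome, the Design section says "After viewing all warnings, participants will complete items on behavioral intentions, perceived risks of waterpipe smoking, and knowledge of risks".

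**The concern.** Six similar ratings in a row may shift with position: the first warning may be novel, and later ones may meet habituation or fatigue. If position is not modelled, any such shift stays in the within-person error of each comparison between warnings, together with chance imbalance in where each warning fell.

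This matters for the third analysis goal. Four of six matched warnings go forward to Aim 3 if they rank consistently high on PME overall and by sex, race/ethnicity, sexual orientation and waterpipe use. Where mean scores are close, avoidable noise can swap ranks, most easily in small subgroups.

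Product appeal raises a related issue. Every control rating is a first-view rating, while an intervention average covers positions 1 to 6. Randomising order within the intervention arms does not make those two alike.

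**Working it through.** **1. The plan's own figures.** Inputs from the Analytical Plan: SD 1.5, correlation 0.6, six measures with compound symmetry, two-sided alpha 0.05, and "For a sample of 400 participants per condition, we will have 80% power".

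- Variance of a six-measure mean: 1.5² × (1 + 5 × 0.6)/6 = 1.5.
- Text versus pictorial: (1.960 + 0.842) × √(2 × 1.5/400) = 0.243 (stated 0.24).
- Warning versus control: (1.960 + 0.842) × √((1.5 + 2.25)/400) = 0.271 (stated 0.27).

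Both reproduce. A position term does not change them. Each complete participant occupies all six positions, so a common position effect adds the same constant to every person's mean. The Design section also places the intentions items after all warnings, so position within the sequence does not apply to them. Whether intentions should be powered as six repeated measures is a separate question.

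**2. Contrast between two warnings within an arm.** The correlation of 0.6 is the plan's planning value for repeated observations. The documents give no PME SD and no position effect, so I assume an SD of 1.2 and a linear drift of b points per position.

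- For a random order of six, Var(position of A − position of B) = 6 × 7/6 = 7.
- Drift variance per person: 7b².
- Other within-person variance: 2 × (1 − 0.6) × 1.2² = 1.152.
- Share due to drift: 7b²/(7b² + 1.152).
- Reduction in SE from adjustment: 1 − √(1.152/(7b² + 1.152)).

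| b | First-to-last shift (5b) | 7b² | Share of variance | SE reduction |
|---|---|---|---|---|
| 0.05 | 0.25 | 0.0175 | 1.5% | 0.8% |
| 0.10 | 0.50 | 0.0700 | 5.7% | 2.9% |
| 0.15 | 0.75 | 0.1575 | 12.0% | 6.2% |

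**3. Other assumed patterns.** With 410 in the arm and correlation 0.6, the SE increase from leaving position out is:

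| Position effect | SD 1.5 | SD 1.0 |
|---|---|---|
| First exposure +0.3 | 0.8% | 1.9% |
| First exposure +0.5 | 2.3% | 5.1% |
| Linear, total 0.3 | 0.7% | 1.6% |
| Linear, total 0.5 | 1.9% | 4.3% |
| Linear, total 1.0 | 7.5% | 16.2% |

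The last row is a steeper trend than any in step 2.

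**4. Bias.** I simulated 410 people, SD 1.5, correlation 0.6 and a 0.5-point linear decline. A true contrast of 0.25 averaged 0.250 both without and with position. The empirical SEs were 0.0675 and 0.0659.

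**5. Absolute size.** The chance difference in mean position between two warnings has SD √(7/n).

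- At n = 410 it is 0.13 positions. With b = 0.10 that is 0.013 points, against a contrast SE of √(1.152/410) = 0.053.
- In an illustrative subgroup of 40 it is 0.42 positions, or 0.042 points, against √(1.152/40) = 0.170.

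The proportion is the same, but the absolute noise is about three times larger.

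**6. Appeal against control.** The mean position in an intervention arm is 3.5 and in control it is 1. Linear drift displaces the comparison by (3.5 − 1) × b = 2.5b. At the three slopes above, taken here as assumed appeal drifts, that is 0.125, 0.25 or 0.375 points on a four-point scale.

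**The case against.** The strongest reply is that randomising the order already removes the threat that matters, because no warning is systematically seen early or late. The rest is conjecture: the documents report no fatigue or novelty effect, the SD and slopes are assumed, and even the largest slope in step 2 changes the SE by only 6%. Nothing shows that a different warning would be chosen, and the selection is a ranking, not a significance test. The covariate list is also open-ended, and since no ranking model is stated, position cannot be said to have been left out of one.

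Most of this stands. A reader might infer that the ranking is biased, that the primary comparison is compromised, or that the plan commits to unadjusted PME scores. The documents support none of these. Order is random, intentions are asked after all warnings, and the text says only that ranks are based on PME scores.

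It would also be wrong to ask for position and condition-by-position in every model. Controls have no positions 2 to 6, so the interaction cannot be estimated for them. Whether a pictorial advantage fades with repeated viewing is not one of the three stated goals.

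Two things remain. The absence of a stated ranking model is a reason to specify one, and the factor to adjust for is already randomised. The reply also does not cover appeal against control, where random order does not equalise position.

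**Conclusion.** The point holds as a minor, near-free improvement. Position is randomised but used in no stated analysis, and the Aim 3 selection rests on PME ranks with no position adjustment stated. The consequence is lost precision in within-arm warning contrasts and rankings, not bias. Adjustment would save about 1% to 6% of the SE for drifts of 0.05 to 0.15 points per position, given a PME SD of 1.2 and a correlation of 0.6. Only the correlation comes from the plan. If there is no position effect, the gain is nil.

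The primary outcome and complete-data text-versus-pictorial averages are unaffected. Comparing control with six-position appeal averages is a narrower issue. It could shift that contrast by 2.5 times the drift, and it arises only if appeal is compared with control and ratings do drift.

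**What to change.** 1. Require NORC to save and deliver the viewing position of each warning for each intervention participant. This should be settled before fielding, because the order may be unrecoverable if the survey program does not store it.
2. In the Analytical Plan, for outcomes rated per warning in the two intervention arms, state a repeated-measures model with warning, condition, warning-by-condition and categorical position (1 to 6). Rank warnings on position-adjusted mean PME, overall and in the named subgroups.
3. Treat condition-by-position as optional and exploratory, in the intervention arms only.
4. For product appeal against control, compare control with the intervention arms' position-1 ratings, at least as a sensitivity analysis. Do not apply the interaction there.

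Items 1 and 2 cost one variable and five degrees of freedom. Item 4 loses precision. With correlation 0.6 and equal arms, one rating per person in place of a six-rating mean widens the SE of the control comparison by a factor of √(2/(1 + (1 + 5 × 0.6)/6)) = √1.2 = 1.095, about 10%. That is a reason to offer it as a sensitivity analysis if the six-rating average is kept as the main one.

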1. How much does this warning grab your attention?

Response scale: (1) Not at all / (2) Very little / (3) Somewhat / (4) Quite a bit / (5) A great deal

Emotional Reactions. Three items to measure negative emotional reactions to the warning that the participant saw. Overall scale scores are determined by summing the scores of the three items and dividing by three.

1. How much does this warning make you feel anxious?
2. How much does this warning make you feel disgusted?
3. How much does this warning make you feel scared?

Response scale: (1) Not at all / (2) Very little / (3) Somewhat / (4) Quite a bit / (5) A great deal

Cognitive Elaboration. One item to measure the extent to which a participant reports the warning making them think about the risks of hookah smoking.

1. How much does this warning make you think about the health effects of smoking hookah?

Response scale: (1) Not at all / (2) Very little / (3) Somewhat / (4) Quite a bit / (5) A great deal

Self-reported Learning. One item to measure the extent to which respondents learned something new from the warning.

1. To what extent did you learn something new from this warning that you did not already know?

Response Scale: (1) Not at all / (2) Very little / (3) Somewhat / (4) Quite a bit / (5) A great deal

Social Interactions. One item to measure self-reported likelihood of discussing the warning shown with one's social contacts within the week following the survey.

1. How likely are you to talk about this warning with others in the next week?

Response Scale: (1) Not at all / (2) Very little / (3) Somewhat / (4) Quite a bit / (5) A great deal

Knowledge. Six items to measure knowledge of the potential health harms described by the warnings.

1. Hookah smoking causes heart damage.
2. Hookah smoking causes lung damage.
3. Hookah smoking causes mouth cancer.
4. Hookah smoking causes carbon monoxide poisoning.
5. Hookah smoking during pregnancy stunts fetal growth.
6. Hookah smoking causes nicotine addiction.

Response scale: (1) True / (2) False / (3) I don't know

Beliefs. Five items to measure the respondent's belief of their own risk of experiencing each of the warning health harms. One item measures risk to pregnant people, rather than the self, since this item will be administered to all participants.

1. If I smoke hookah, I will damage my heart.

2. If I smoke hookah, I will damage my lungs.
3. If I smoke hookah, I will get mouth cancer.

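### Does Product Appeal need a scoring rule, a block order and a rule for six ratings against one before it can be compared with control?

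*Combined protocol and SAP*

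**What the plan says.** Under Interventions and Interactions, each warning-arm participant sees six packages, "each with a different warning corresponding to their condition, in random order, and will complete items on package appeal and warning perceptions". For control, "Participants in the control condition will be shown one waterpipe package with no warning on it and will complete items on package appeal". The Design section gives the same structure: intervention "participants will respond to measures designed to assess their warning reactions (emotional and cognitive reactions, perceived message effectiveness), and appeal of each package", while "Control group participants will complete items on package appeal". It then places the later outcomes: "After viewing all warnings, participants will complete items on behavioral intentions, perceived risks of waterpipe smoking, and knowledge of risks".

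Under Outcome Measure(s), Product Appeal is listed among the Other outcomes. It has three numbered items on a 1 to 4 scale: how appealing the product is, how likely the respondent would be to try it, and "How much does this packaging make you think this product is harmful". No sentence says how they are scored. The other three-item measures do have a rule. Intentions are averaged. For perceived message effectiveness (PME), "Overall scores are determined by summing the scores of the three items and dividing by three". For emotional reactions, "Overall scale scores are determined by summing the scores of the three items and dividing by three".

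The Analytical Plan fits condition as a fixed effect in PROC MIXED, allowing for weights and repeated measures. It gives a detectable difference of 0.27 (effect size 0.18) for a warning arm against a control arm without repeated measures. Similar separate models are planned for behavioral antecedents, introduced by an open list of examples that does not name Product Appeal.

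**The concern.** Every other per-package question asks about a warning, so control participants can answer only the appeal items. Product Appeal is therefore the one per-package outcome that can be compared across all three arms, and four details of that comparison are left open.

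- **Score.** The other three-item measures are averaged. An analyst who followed that pattern literally would average appeal and perceived harm with opposite signs, which would shrink, cancel or reverse the arm difference. This would affect pictorial versus text as well as contrasts with control.
- **Six ratings against one.** Any change over successive views enters the six-view mean and is absent from the single control rating.
- **Block order.** Design lists warning reactions and then appeal; Interventions and Interactions lists appeal and then warning perceptions. If appeal comes second, even the first warning-arm rating follows questions that control participants never receive.
- **Meaning of the control contrast.** Warning arms view and rate six packages before the later outcomes, and control views one. Those contrasts estimate the effect of viewing and rating six warnings, not of warning presence alone.

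**Working it through.** **Inputs.** From the Analytical Plan: 400 per condition, 80% power, two-sided 5% level, SD 1.5, six repeats with compound symmetry, correlation rho = 0.6. From Design: about 410 per arm. The sum of the two normal quantiles (97.5% and 80%) is 2.8016.

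**Amount of data.** Rating sets per arm: 410 × 6 = 2,460 in a warning arm, and 410 × 1 = 410 in control.

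**The plan's own figures.** In SD units, the variance of one person's mean of six ratings is m = (1 + 5 × 0.6)/6 = 0.667.

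- Text versus pictorial: 2.8016 × √(2 × 0.667/400) = 0.162, and × 1.5 = 0.243 (stated 0.24).
- Warning arm versus control: 2.8016 × √((0.667 + 1)/400) = 0.181, and × 1.5 = 0.271 (stated 0.27).
- One rating against one would give 2.8016 × √(2/400) = 0.198, and × 1.5 = 0.297, which does not match.

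So the stated 0.27 implies a mean of six correlated ratings against one control rating. The statement is written for intentions, but it describes the data structure that Product Appeal has.

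**What the choice of control comparison changes.** Detectable effects in SD units at n = 400. The plan gives no correlation for Product Appeal, so rho from 0.4 to 0.8 is an assumption.

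| Analysis | Variance term | rho 0.4 | rho 0.6 | rho 0.8 |
|---|---|---|---|---|
| Mean of six views | m = (1 + 5 rho)/6 | 0.172 | 0.181 | 0.190 |
| Linear view-position term, contrast at view 1 | p = m + 2.5² × (1 − rho)/17.5 | 0.183 | 0.188 | 0.193 |
| First view only | 1 | 0.198 | 0.198 | 0.198 |

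Each entry is 2.8016 × √((variance term + 1)/400). The view-position term is 2% to 7% less precise than the six-view mean, and the first view alone 4% to 15% less. The analysis implied by the plan is the most precise of the three.

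**Scoring.** Assume that a warning lowers items 1 and 2 by d each and raises the harm item by k × d.

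- Harm item reversed: the mean changes by −(2 + k)d/3.
- Harm item not reversed: the mean changes by −(2 − k)d/3.
- Share kept: (2 − k)/(2 + k), which is 60% at k = 0.5, 33% at k = 1, 0% at k = 2 and −20% at k = 3.

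The sign flips only if the harm item moves more than twice as far as each of the others. The documents give no value of k. If the items are analysed separately, the problem does not arise.

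**Block order.** The two sections list the question blocks in summary prose joined by a conjunction; neither states a sequence, so they do not contradict each other. The three appeal items are numbered and the packages come in random order. The survey vendor programs the questionnaire, which is not among the documents, so its block order cannot be judged here.

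**The case for a change.** The best case for a change is the score. Of the four three-item measures, Product Appeal is the only one without an averaging rule and the only one with an item pointing the other way. Fixing the score in advance would take a sentence and would remove a choice otherwise open after results are seen. The control contrast could likewise be labelled, and a view-position sensitivity analysis added, without loss of precision in the main model, provided view order is stored.

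The factual part stands: there is no scoring sentence, the model is not expressly assigned to Product Appeal, and block order is not stated. The consequence does not follow. Where the plan wants an average it says so. It describes Product Appeal as covering three different things, so item-by-item analysis is at least as natural a reading. An analyst who did combine them would see from the wording that the harm item must be reversed. The six-against-one structure is covered by the repeated-measures model and implied by the power statement. The unequal exposure is stated openly in two sections, and randomisation keeps the contrasts valid. The view-position analysis would guard against a drift for which the documents give no size or direction.

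**Conclusion.** No change follows. This is missing detail on an outcome listed under Other, of a kind that analysts fill sensibly: analyse the harm item separately or reverse it, and use all six ratings in the mixed model. The plan's 0.27 reproduces (0.271) on a six-against-one basis. The scoring loss, for example to 33% of the difference at k = 1, requires both a composite that the plan does not announce and a failure to reverse an obviously opposed item; k itself is assumed. No bias from repeated viewing or block order can be shown from the documents.

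Exposure and rating load are equal in the text and pictorial arms, so the stated hypothesis is unaffected. The choice of warnings for Aim 3 rests on PME, not on appeal. Describing contrasts with control as the effect of viewing and rating six warnings is a matter of careful reporting. This conclusion assumes ordinary competence in scoring the three items; it does not depend on the assumed correlations.

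### The plan relies on PROC MIXED to handle the sample weights but names neither a robust variance nor a covariance structure; with default output, either the standard error is too small or the weighting is lost

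*Combined protocol and SAP*

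**What the plan says.** The Analytical Plan is the only description of the analysis. For waterpipe smoking intentions it says "we will fit a linear regression model using PROC MIXED in SAS to account for the sampling design features (e.g., sample weights, repeated measures"). Condition is then a fixed effect, with and without covariate adjustment, and tests are two-sided. The significance level is fixed for every comparison: "For all comparison, the correlation between repeated observations on the same subject is 0.6 and the alpha level is 0.05". Models for the behavioral antecedents are to be fitted "using separate models, similar to those described above for WTS intentions".

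The Design section says the panel vendor will deliver a final dataset "where participants are weighted to create a nationally representative sample". The participants come "from a combination of their AmeriSpeak panel (approximately N=1000) and a third-party opt-in panel (remainder"), and Subject Selection Criteria describes the second source as "a third-party non-probability sample, weighted with the AmeriSpeak sample to be nationally representative".

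On timing, the Design section says: "After viewing all warnings, participants will complete items on behavioral intentions, perceived risks of waterpipe smoking, and knowledge of risks". As described there, intentions give one score per person.

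No section names a robust, empirical, linearised or replicate variance, a survey procedure, a RANDOM or REPEATED statement, a design effect or a weight-trimming rule.

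**The concern.** The WEIGHT variable in PROC MIXED tells the model that an observation with weight w has residual variance σ²/w. A sampling weight says something else: how many people in the population the respondent stands for. It carries no information about how noisy that person's answer is. Without a further option, the procedure reads the second kind of weight as the first.

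The consequence depends on a model choice that the plan leaves open. If the weight scales the whole error term (ordinary weighted regression, or a REPEATED structure), the estimate is the intended weighted mean difference, but its default standard error ignores the precision lost through unequal weights. If a random intercept is added, the weight scales only the residual and the intercept variance is unweighted. The standard error is then about right, but the estimate is almost unweighted.

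In the first case the text-versus-pictorial test does not hold its 0.05 level and its 95% interval is too narrow. In the second, a result presented as weighted to the nation is not. The antecedent models inherit the same gap.

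**Working it through.** **Inputs from the documents.** Two-sided alpha 0.05; SD 1.5; six repeats, compound symmetry, correlation 0.6; 400 per condition for power, about 410 randomized per condition; about 1,000 panel members and 1,230 − 1,000 = 230 opt-in. **Not in the documents:** the weights. Every design effect (DEFF = 1 + CV² of the weights) is assumed.

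**1. The plan's own figures.** Variance factor for a mean of six repeats: (1 + 5 × 0.6)/6 = 0.667.
- Text versus pictorial: (1.960 + 0.842) × 1.5 × √(2 × 0.667/400) = 0.243 (stated 0.24). Power at 0.24 is 79.1%.
- Warning versus control: 2.802 × 1.5 × √((0.667 + 1)/400) = 0.271 (stated 0.27).

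Both reproduce, and neither contains a design effect.

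**2. Ordinary weighted fit, one score per person, default standard error.** If weights are unrelated to residual variance, the default variance of an arm mean is about σ²/n and the true variance is (σ²/n) × DEFF. The actual two-sided level is 2 × Φ(−1.96/√DEFF). With 410 per arm the reported 95% half-width is 1.96 × 1.5 × √(2/410) = 0.205. The correct one is 0.205 × √DEFF.

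| Assumed DEFF | Type I error | Coverage of nominal 95% CI | Correct half-width |
|---|---|---|---|
| 1.1 | 6.2% | 94% | 0.215 |
| 1.25 | 8.0% | 92% | 0.230 |
| 1.5 | 11.0% | 89% | 0.251 |
| 2.0 | 16.6% | 83% | 0.290 |

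Simulation (20,000 replicates, log-normal weights) gave 6.4%, 7.8%, 11.0% and 16.6% with default standard errors. A sandwich standard error gave 4.9% to 5.2%.

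**3. Weights related to residual variance.** If variance is proportional to w^a and weights are log-normal, true over default variance is E[w^(2+a)]/(E[w] × E[w^(1+a)]) = DEFF^(1+a). At DEFF 1.5:
- a = −1: ratio 1, type I error 5%.
- a = −0.5: ratio 1.22, 7.7%.
- a = 0: ratio 1.5, 11.0%.
- a = +0.5: ratio 1.84, 14.8%.

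Simulations gave about 7% to 8% for a = −0.5 and 14% to 17% for a = +0.5.

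**4. Random-intercept fit, default standard error.** A person's variance is τ² + σ²/w, so the effective weight is 1/(τ² + σ²/w). With one row per person, simulation by REML (4,000 runs, Monte Carlo SE about 0.35 points) gave type I error of 5.8%, 4.8%, 5.0% and 5.1% at DEFF 1.1, 1.25, 1.5 and 2.0. The DEFF of the effective weights was only about 1.001.

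**5. Outcomes with six rows per person.** At the same four DEFF values (5,000 replicates, correlation 0.6), REPEATED compound symmetry with default standard errors gave 6.3%, 7.9%, 9.9% and 17.5%. A random intercept gave 4.8%, 5.1%, 4.7% and 5.2%, with an effective-weight DEFF of 1.001 to 1.019. The reason is visible in the plan's own variance: τ² = 0.6 × 2.25 = 1.35 and σ²/6 = 0.4 × 2.25/6 = 0.15. A person with w = 2 gets 1/(1.35 + 0.075) = 0.702; one with w = 0.5 gets 1/(1.35 + 0.30) = 0.606. A fourfold weight ratio shrinks to 1.16.

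**6. What the documented split alone gives.** Assume equal weights within source and an opt-in to panel weight ratio r. Then DEFF = 1230 × (1000 + 230r²)/(1000 + 230r)².
- r = 0.5: DEFF 1.05, type I error 5.5%.
- r = 2: DEFF 1.11, 6.3%.
- r = 3: DEFF 1.32, 8.8%.

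Demographic calibration is not included. These calculations code precision weighting directly; SAS itself was not run.

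**The case against.** The strongest reply is that this is an omission and not a stated error. The plan never says that default standard errors will be used, and PROC MIXED with the EMPIRICAL option and a REPEATED structure is a valid weighted analysis. SAS options can still be settled before the data arrive. That stands: a reader might infer that the primary test as planned is invalid, and the documents do not support that. They support only that the text does not exclude an invalid analysis, and that an analyst who follows it literally with default output would get one.

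A second reply is that default standard errors with unequal weights do not always inflate type I error. This also stands. A random-intercept fit holds about 5% even with one row per person, and a fit in which variance is truly proportional to 1/w has no excess. But the random-intercept fit keeps its level by discarding the weights, which defeats the stated purpose, and nothing in the documents suggests that these weights track inverse variance.

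A third reply is that the excess could be small. At a DEFF of 1.05 it is half a percentage point. Neither the 17% nor any other single figure should be read as the expected error. The documents give reason to expect unequal weights, because an opt-in sample is weighted jointly with a probability panel, but no measure of how unequal.

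**Conclusion.** The point holds as an unspecified variance estimator and covariance structure in a procedure whose default does not suit sampling weights. With unequal weights and default standard errors, the once-per-person primary analysis either understates its standard error (ordinary weighted or REPEATED fit) or loses its weighted target (random intercept).

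The 6% to 17% range belongs to the first branch only. It assumes DEFF between 1.1 and 2.0 and weights unrelated to residual variance; the excess is smaller if variance falls as the weight rises, and larger if variance rises with it. The only calculation tied to a documented count, the 1,000 + 230 split, gives 5.5% to 8.8% under assumed weight ratios of 0.5 to 3. A general claim that type I error exceeds 5% whenever default standard errors meet unequal weights would be too strong.

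Whether the plan is right to treat intentions as a repeated measure is a separate question, not decided here. It should be fixed before analysis; confidence is moderate because the realised weights are unknown.

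**What to change.** Add one or two sentences to the Analytical Plan that cover all weighted models:

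- Use PROC SURVEYREG with the weight and participant as CLUSTER, plus strata or sampling units if the panel vendor supplies them; or keep PROC MIXED with EMPIRICAL, SUBJECT=participant and a REPEATED structure.
- Do not use a random-intercept fit as the weighted analysis.
- Report the realised design effect.

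Design, sample and estimand do not change. The price is wider intervals and less power than stated. Effective n per arm is 410/DEFF: about 373, 328, 273 and 205 at DEFF 1.1, 1.25, 1.5 and 2.0. Under the plan's own six-repeat assumption with 400 per arm, power at 0.24 is about 62% at DEFF 1.5 and 50% at DEFF 2.0, against 79% without weighting. With one score per person the same figures are 46% and 36%, against 62%. This loss comes from the weighting itself; default standard errors would only hide it.
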